1.2 Summary and Rationale

In clinical practice, the FDA approved the Pfizer-BioNTech and Moderna COVID-19 vaccines and granted an Emergency Use Authorization for Janssen COVID-19 vaccine in February 2021. Hence, vaccines for both COVID-19 and influenza prevention have the potential for being administered at the same time seasonal influenza vaccine is available. In the pre-licensure efficacy studies, neither the Pfizer-BioNTech or Moderna mRNA vaccines were evaluated for either safety or immunogenicity when co-administered with a non-COVID-19 vaccine. The Phase 3 trial of the AstraZeneca chimpanzee adenovirus-vectored COVID-19 vaccine did not prohibit influenza vaccination but simultaneous administration was not systematically evaluated. Initial guidance from the CDC stated that COVID-19 vaccines should be given alone with at least 14 days either before or after receipt of any other vaccines, including an influenza vaccine, because of limited information on the safety and effectiveness of co-administration. Current guidance now states that COVID-19 vaccines can be administered on the same day as other vaccines but mentions that it is unknown if simultaneous administration will affect reactogenicity^{17,37,40}. A single study has assessed the safety and immunogenicity of a 3rd dose of Moderna's mRNA COVID-19 vaccine and High-Dose quadrivalent influenza vaccine when administered simultaneously to adults 65 years and older. No safety concerns or immune interference were observed.⁴¹

Due to the potential for severe influenza complications and resulting morbidity and mortality, it remains particularly important that influenza vaccine is encouraged for all persons 6 months of age and older without any contraindications. Likewise, as the pandemic continues and COVID-19 vaccines become available it is critically important that their use be encouraged in those populations for whom there is an authorization and an ACIP recommendation. To date, we are unaware of any studies evaluating the safety and immune responses following concomitant administration of both mRNA COVID-19 and influenza vaccines in a more general population. Hence, we aim to study the safety of simultaneous versus sequential administration of mRNA COVID-19 vaccine and IIV4. Participants receiving mRNA COVID-19 vaccines as either standard of care or a study procedure will be randomized to receive either IIV4 or placebo within 8 hours of their initial dose of mRNA COVID-19 vaccine. Those receiving IIV4 will receive placebo 14 days later and those receiving placebo will receive IIV4 14 days later.

We have elected to evaluate the mRNA COVID-19 vaccines for evaluations for three reasons: 1) there is greater accumulated experience with using mRNA COVID-19 vaccines in the population; 2) the different reactogenicity profiles for the mRNA COVID-19 vaccines as compared to the Janssen adenoviral vector COVID-19 vaccine decreases the ability of a single small study to address the question of co-administration safety¹³ and 3) the preferential recommendation for the use of mRNA COVID-19 vaccines over the Janssen vaccine for both primary and booster vaccination due to concerns related to thrombosis with thrombocytopenia syndrome following Janssen COVID-19 vaccine⁴². In addition, we hope to assess the effects of

pre-existing COVID-19 antibody before vaccination on the occurrence of vaccine side effects and to assess the effects of COVID-19 vaccine administration on IIV4 immunogenicity.

The current protocol allows for inclusion of persons receiving a booster dose of mRNA COVID-19 vaccine. Administration of booster dose mRNA COVID-19 vaccines to participants who are enrolled in this protocol, will adhere to current FDA prescribing recommendations for licensed or EUA mRNA COVID-19 vaccines and to ACIP recommendations for their use as the approvals and recommendations are made. Inclusion of persons receiving a booster dose of COVID-19 vaccine will allow for enhanced recruitment during the influenza vaccination season in which it is expected that most adults and many children receiving an mRNA COVID-19 vaccine in this study will be receiving a booster dose rather than an initial vaccine two-dose series.

2 STUDY OBJECTIVES AND OUTCOME MEASURES

OBJECTIVE	OUTCOME
Primary	
1. To compare the proportion of participants with moderate or more severe fever, chills, myalgia, or arthralgia in the group receiving IIV4 simultaneously with mRNA COVID-19 vaccine at Vaccination Visit 1 (Simultaneous group) with the group receiving IIV4 alone one to two weeks later at Vaccination Visit 2 (Sequential group) following both Vaccination Visit 1 and 2 Hypothesis: The proportion of participants with moderate or more severe fever, chills, myalgia or arthralgia will be noninferior (not higher) in the Simultaneous group versus the Sequential group.	1a. Comparison of the proportion of participants reporting at least one solicited reactogenicity event to include fever, chills, myalgia, or arthralgia of moderate or greater severity in the Simultaneous group with the Sequential group within 1-7 days following both Vaccination Visit 1 and Vaccination Visit 2
Secondary	
1. To compare the proportion of participants with moderate or more severe fever, chills, myalgia, or arthralgia in the Simultaneous versus the Sequential Group following the first vaccination visit	1a. Comparison of the proportion of participants reporting at least one solicited reactogenicity event to include fever, chills, myalgia, or arthralgia of moderate or greater severity in the Simultaneous group with the Sequential group within 1-7 days following Vaccination Visit 1 visit during which participants receive either IIV4 or placebo with an mRNA COVID-19 vaccine

2. To compare the proportion of participants with moderate or more severe fever, chills, myalgia, or arthralgia in the Simultaneous versus Sequential Group following the second vaccination visit	2a. Comparison of the proportion of participants reporting at least one solicited reactogenicity event to include fever, chills, myalgia, or arthralgia of moderate or greater severity in the Simultaneous group with the Sequential group within 1-7 days following Vaccination Visit 2 during which participants receive either IIV4 or placebo without an mRNA COVID-19 vaccine
3. To describe the proportions of participants in the Simultaneous and Sequential vaccination groups with solicited local and systemic reactogenicity events according to severity grade after the first and second vaccination visit and third vaccination visit for those receiving two doses of mRNA COVID-19 vaccine	3a. The proportion of participants in each vaccination group reporting specified solicited local and systemic reactogenicity events of any severity and by severity grade within 1-7 days following the first vaccination visit during which participants receive either IIV4 or placebo with an mRNA COVID-19 vaccine 3b. The proportion of participants in each vaccination group reporting specified solicited local and systemic reactogenicity events of any severity and by severity grade within 1-7 days following the second vaccination visit during which participants receive either IIV4 or placebo 3c. The proportion of participants in each vaccination group reporting specified solicited local and systemic reactogenicity events of any severity and by severity grade within 1-7 days following the third vaccination visit during which all participants receive an mRNA COVID-19 vaccine alone for those receiving two doses of mRNA COVID-19 vaccine
4. To describe the proportions of participants in the Simultaneous and Sequential vaccination groups experiencing at least one serious adverse event and a description of these events	4a. The proportion of participants in Simultaneous and Sequential Groups with at least one serious adverse event occurring during the study period and a description of each event

Exploratory	

1. To compare the proportion of participants with moderate or more severe fever, chills, myalgia, or arthralgia in the Simultaneous versus Sequential Group following the third vaccination visit for those receiving two doses of mRNA COVID-19 vaccine
	
1a. Comparison of the proportion of participants reporting at least one solicited reactogenicity event to include fever, chills, myalgia, or arthralgia of moderate or greater severity in the Simultaneous group with the Sequential group within 1-7 days following Vaccination Visit 3 during which all participants receive an mRNA COVID-19 vaccine alone for those receiving two doses of mRNA COVID-19 vaccine


2. To further characterize and describe the proportion of participants in the Simultaneous and Sequential groups with local or systemic reactogenicity events of greater severity following each vaccination visit and cumulatively
	
2a. The proportion of participants reporting at least one moderate or greater or at least one severe or greater solicited local or systemic reactogenicity event in each vaccination group within 1-7 days following the first vaccination during which participants receive either IIV4 or placebo with an mRNA COVID-19 vaccine
 
2b. The proportion of participants reporting at least one moderate or greater or at least one severe or greater solicited local or systemic reactogenicity event in each vaccination group within 1-7 days following the second vaccination visit which participants receive either IIV4 or placebo
 
2c. The proportion of participants reporting at least one moderate or greater or at least one severe or greater solicited local or systemic reactogenicity event in each vaccination group within 1-7 days following the third vaccination visit during which all participants receive an mRNA COVID-19 vaccine alone for those receiving two doses of mRNA COVID-19 vaccine
 
2d. The proportion of participants reporting at least one moderate or greater or at least one severe or greater solicited local or systemic reactogenicity event in each vaccination group within 1-7 days following all vaccination visits combined

3. To describe the proportion of participants in Simultaneous and Sequential groups experiencing at least one unsolicited adverse event and one adverse event of special interest and to characterize these events	
3a. The proportion of participants in each vaccination group with an unsolicited adverse event occurring during the 7 days post each vaccination visit according to severity and system organ classification
 
3b. The proportion of participants in each vaccination group with an adverse event of special interest occurring during the study period according to event type

4. To compare the change of health-related quality of life (HRQOL) from baseline in the Simultaneous versus Sequential groups following the Vaccination Visit 1	4a. Comparison between vaccination groups of the mean maximal change in score from baseline on the EuroQOL 5 dimensions-5 level (EQ-5D-5L) and EuroQOL visual analogue scale (EQ VAS) within 1-7 days following the first vaccination visit
5. To assess the safety profiles in the simultaneous and sequential group participants by baseline COVID-19 serostatus	5a. To compare secondary outcomes 3a, 3b, 3c, and 4a according to baseline COVID-19 serostatus
6. To assess the safety profiles in the simultaneous and sequential group participants by vaccine product (Pfizer or Moderna).	6a. To compare secondary outcomes 3a, 3b, 3c, and 4a according to vaccine product (Pfizer or Moderna).
7. To assess the effect of simultaneous administration of IIV4 and COVID-19 vaccine on IIV4 immunogenicity as assessed by hemagglutination inhibition assay (HAI)	
7a. The proportion of participants in each vaccination group with a seroprotective HAI titer ($\geq 1:40$) pre- and post-IIV4 immunization for each IIV4 antigen
 
7b. The proportion of participants in each vaccination group achieving seroconversion following IIV4 (an HAI titer $\geq 1:40$ following IIV4 if the baseline titer is $< 1:10$ or a four-fold rise in HAI titer if the baseline titer is $\geq 1:10$) for each IIV4 antigen
 
7c. The geometric mean HAI titer (GMT) for each IIV4 antigen pre- and post-IIV4 in each vaccination group
 
7d. The geometric mean fold rise (GMFR) in HAI titer for each vaccination group

8. To assess serum antibody levels to SARS-CoV-2 antigens	8a. The proportion of participants in each vaccination group seropositive to SARS-CoV-2 variants tested prior to and following mRNA COVID-19 vaccine

	8b. The geometric mean ID ₅₀ and ID ₈₀ titers of neutralizing antibodies for each SARS-CoV-2 variant tested pre- and post-mRNA COVID-19 vaccine in each vaccination group
--	---

3 STUDY DESIGN

3.1 Main study design

This study is a prospective, randomized, clinical trial to assess the safety of simultaneous versus sequential administration of mRNA COVID-19 and IIV4 vaccines in 450 persons age ≥ 5 years enrolled at Duke University Medical Center (Lead Contractor), Johns Hopkins University (Contributing Contractor), and Cincinnati Children's Hospital Medical Center (Contributing Contractor). Participants will be enrolled in the 2021-2022 and 2022-2023 influenza seasons. Individuals will be enrolled who have not received their influenza vaccine during the influenza season during which they are recruited and are either receiving a booster dose of mRNA COVID-19 vaccine (for ages booster is authorized and recommended) or are receiving a primary two-dose mRNA COVID-19 vaccine series (5 years of age or older). Future mRNA COVID vaccines may include SARS-CoV-2 viral variants which may be included in this study if authorized or approved by the FDA and recommended by the CDC. Health, demographic and health-related quality of life (HRQOL) data will be collected from study participants 12 years of age or older at baseline. All participants receiving an mRNA COVID-19 vaccine on Day 1 (Visit 1) will be randomized to receive quadrivalent inactivated influenza vaccine (IIV4) or placebo. Persons aged < 65 years will receive standard dose IIV4 (SD-IIV4) or saline placebo injection. To qualify for the study, children < 9 years of age must only need to receive a single dose of IIV4 per ACIP recommendations for the 2022-2023 season. Persons aged ≥ 65 years will receive high-dose IIV4 (HD-IIV4) or saline placebo injection. Participants will receive the vaccines in an observer-blinded manner on the same day as they receive mRNA COVID-19 vaccine. Seven to fourteen days later (Visit 2) those who received IIV4 at Visit 1 will receive placebo and those who received placebo on at Visit 1 will receive IIV4 (SD-IIV4 or HD-IIV4, depending upon age). Participants will then receive a second mRNA COVID-19 vaccine (Visit 3), if applicable, and according to the recommended schedule for vaccination for the respective mRNA COVID-19 vaccine product used.

With Day 1 serving as the initial day of vaccination, participants will be followed through Day 7 (total 7 days) for solicited symptoms of reactogenicity as described in Section 5.4. HRQOL data will be collected during this time period for persons aged ≥ 12 years. Solicited reactogenicity events will also be monitored through Day 7 (total 7 days) following Visit 2 (all participants) and Visit 3 (only those participants receiving primary 2-dose COVID-19 vaccine series). Participants will also be followed for 7 days after each vaccination visit for unsolicited adverse events, through Day 120 for serious adverse events (SAEs) and through Day 120 for adverse events of special interest (AESI), as described in Section 5.4.

3.2 Laboratory Studies

3.2.1 Influenza Hemagglutination Inhibition Assay

mRNA COVID-19 vaccine naïve participants will have blood draws on Day 1 (before vaccination) and Day 21 (2021-2022 season) or Day 29 (2022-2023 season) (Pfizer/BioNTech mRNA vaccine) or Day 29 (Moderna mRNA post-IIV4 vaccination to be stored for serum hemagglutination inhibition (HAI) antibody titers. Those receiving a booster dose of mRNA COVID-19 vaccine will have blood draws on Day 1 (before vaccination) and Day 29. HAI antibody titers will be compared between groups receiving COVID-19 and IIV4 simultaneously or sequentially for each of the four influenza vaccine strains contained in the respective vaccines for that season. Participants will not receive individual HAI antibody titer results; these are not routinely used in clinical practice.

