6.2 Influenza Hemagglutination Inhibition (HAI) Assay

Influenza Hemagglutination Inhibition (HAI) Assays will be performed on sera collected, contingent on additional funding. Briefly, reference wild-type, reassortant, or vaccine virus strains representative of the specific viral antigens included in the 2021-22 influenza vaccine will be used to evaluate the relative levels of all four influenza strain-specific antibodies in

participant serum samples collected pre- and 21 or 28 days post-vaccination from all study participants. To accomplish these activities, all participant samples will be interrogated for influenza antibodies against the strains of interest using the influenza hemagglutination inhibition assay (HI). This assay is considered the “gold-standard” measure by which to evaluate seroconversion/seroprotection in response to seasonal influenza vaccination. This assay will be performed in accordance with the Duke Regional Biocontainment Laboratory Virology Unit’s fully optimized and approved SOP (RVUSOP004 Influenza HI of Serum Samples). Briefly, test samples will be assayed by HAI as duplicate 2-fold dilution series starting at 1:10. Serum dilutions are then incubated with a concentration of virus verified to possess a known potential for red blood cell (RBC) agglutination. The presence of virus-specific antibodies is visualized via incubation of the virus-serum mixture with a RBC solution; the endpoint titer for a given dilution series is then expressed as the reciprocal of the final dilution in which complete HAI is observed. By convention, seronegative samples are defined as having an endpoint HAI titer < 40 and seropositive samples as having an endpoint titer of $\geq 1:40$; and seroconversion as a 4-fold change in endpoint titer relative to pre-immunization baseline or a change from <10 to $\geq 1:40$ ⁵¹.

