### 4.2 Laboratory

#### 4.2.1 Influenza Hemagglutination Inhibition Assay

mRNA COVID-19 vaccine naïve participants will have blood draws on Day 1 (before vaccination) and Day 29 (Pfizer/BioNTech mRNA vaccine) and (Moderna mRNA vaccine) post-IIV4 vaccination to be stored for serum hemagglutination inhibition (HAI) antibody titers. Those receiving a booster dose of mRNA COVID-19 vaccine will have blood draws on Day 1 (before vaccination) and Day 29. HAI antibody titers will be compared between vaccination groups receiving COVID-19 and IIV4 simultaneously or sequentially for each of the four influenza vaccine strains contained in the respective vaccines for that season. Participants will not receive individual HAI antibody titer results; these are not routinely used in clinical practice.

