#### **6.3 Immunogenicity Population**

This population defined as subjects who received vaccine, provide baseline and Visit 3 and Visit 4 blood draws of acceptable volume and quality within the protocol-defined time frame for the respective vaccine with no protocol violations affecting immunogenicity. Protocol violations affecting the immunogenicity analyses are defined in the Statistical Analysis Plan (SAP) Appendix 1. The acceptable visit window for sample analysis will be -7/+14 days from the target date. Any subject with sufficient data for either or both of the influenza and SARS-CoV-2 analysis will be included in this population. Should 10% or more of the total study population be excluded from the Immunogenicity Population due to missing the visit window,

then an additional analysis will be performed including these subjects with the missing visit window exclusion.

The Full Analysis Population 1 is the primary population for analysis unless otherwise stated.

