The proportion of participants in each vaccination group with a seroprotective HAI titer ( $\geq 1:40$ ) pre- and post-IIV4 immunization for each IIV4 antigen will be compared using a Mantel-Haenszel statistic in a stratified analysis by site to control for the randomization blocks at the two-sided alpha 0.05 level.

The proportion of participants in each vaccination group achieving seroconversion following IIV4 (an HAI titer  $> 1:40$  following IIV4 if the baseline titer is  $< 1:10$  or a four-fold rise in HAI titer if the baseline titer is  $> 1:10$ ) for each IIV4 antigen will be compared using a Mantel-Haenszel statistic in a stratified analysis by site to control for the randomization blocks at the two-sided alpha 0.05 level.

The geometric mean HAI titer (GMT) for each IIV4 antigen pre- and post-IIV4 in each vaccination group will be compared (within vaccine group pre versus post and between vaccination groups) using a regression model with the log transformed titer value at the two-sided alpha 0.05 level. The geometric mean fold rise (GMFR) in HAI titer for each vaccination group will be presented along with a 95% confidence interval.

The Immunogenicity Population is the primary analysis population.

8. EO8: Assessments of the serum antibody levels to SARS-CoV-2 antigens.

The proportion of participants in each vaccination group seropositive to SARS-CoV-2 variants tested prior to and following mRNA COVID-19 vaccine will be compared using a Mantel-Haenszel statistic in a stratified analysis by site to control for the randomization blocks at the two-sided alpha 0.05 level. Comparisons will be made pre- and post-vaccination for each variant tested. The definition of seropositive is as follows:

- $ID_{50}$  above Limit of Detection (LOD) at baseline
- after vaccination and seronegative at baseline,  $ID_{50}$  above LOD is considered seropositive
- after vaccination and seropositive at baseline, then an  $ID_{50}$  3-fold over baseline  $ID_{50}$  is considered seropositive.

The term  $ID_{50}$  refers to the inhibitory dilution where 50% neutralization occurs, and  $ID_{80}$  refers to the inhibitory dilution where 80% neutralization occurs.  $ID_{50}$  estimates are generally used for analysis purposes since they are in the linear part of the curve and more stable estimates.

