### Major Protocol Violations for Influenza and SARS-CoV-2 Immunogenicity Analysis

1. Major Protocol Violations for Exclusion from Immunogenicity Populations:
  - a. Not all study vaccines received
  - b. No pre- and/or post-vaccination blood draw or insufficient volume for assay analysis for respective vaccine\*
  - c. Receipt of any other vaccine between the pre- and post-vaccination blood draws
  - d. New immunosuppression disorders between the pre- and post-vaccination blood draws or receipt of immunosuppressive medication between the pre- and post-vaccination blood draws
  - e. Subject who was inadvertently enrolled and randomized to the study, though they were later learned to have had met the following criteria (see f-k below) for study exclusion that would have affected immunogenicity
  - f. Influenza vaccine receipt during the current influenza season prior to study enrollment
  - g. COVID-19 vaccine prior to enrollment unless presenting for a booster dose
  - h. Prior receipt of non-mRNA COVID-19 vaccine
  - i. Use of oral or parenteral corticosteroids ( $\geq 20\text{mg/day}$  prednisone equivalent) or high-dose inhaled glucocorticoid for  $\geq 14$  consecutive days within the preceding 30 days
  - j. Has an active neoplastic disease (excluding non-melanoma skin cancer), a history of any hematologic malignancy
  - k. Has a history of receiving immunoglobulin or other blood product (with exception of Rh immunoglobulin) within the 3 months prior to study vaccination or during the study including Evushield or other COVID-19 monoclonal antibody.
  - l. Subject who was enrolled for both the 2021-22 and 2022-23 flu seasons may be included in immunogenicity for the 2021-2022 season only.

\*Blood draws will not be considered out of window as long as blood was collected within -7/+14 days of the protocol window for the respective vaccine

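### The SAP omits the first-season Day 21 HAI draw for BNT162b2 primary-series participants, words the sample window two ways, and does not say how the two seasons are combined

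*Protocol*

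**What the plan says.** **Draw day.** Protocol 3.2.1 gives participants starting a BNT162b2 primary series a post-vaccination HAI draw at "Day 21 (2021-2022 season) or Day 29 (2022-2023 season) (Pfizer/BioNTech mRNA vaccine"). Booster recipients have one schedule throughout: "Those receiving a booster dose of mRNA COVID-19 vaccine will have blood draws on Day 1 (before vaccination) and Day 29". Protocol 6.2 describes the sera in elapsed time, as "participant serum samples collected pre- and 21 or 28 days post-vaccination". SAP 4.2.1 covers the same draws but gives only "Day 29 (Pfizer/BioNTech mRNA vaccine) and (Moderna mRNA vaccine) post-IIV4 vaccination", although SAP 4.1 says that both seasons are in the study.

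**Sample window.** SAP 6.3 says "The acceptable visit window for sample analysis will be -7/+14 days from the target date", without naming the target. The same section requires draws "within the protocol-defined time frame for the respective vaccine with no protocol violations affecting immunogenicity". The Appendix 1 footnote accepts blood collected "within -7/+14 days of the protocol window for the respective vaccine".

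**Analysis.** SAP 8.3, EO7, compares HAI geometric means "using a regression model with the log transformed titer value at the two-sided alpha 0.05 level" and lists no covariates. The EO8 regression adjusts for vaccine platform and site. The Mantel-Haenszel tests in both objectives are stratified by site. Influenza season appears only among the baseline items in SAP 7.1.

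**The concern.** SAP version 1.0 is dated 3/2/2023, after the first season's draws. A programmer who works from the SAP alone finds one target, Day 29, and may apply it to samples that the protocol scheduled for Day 21. A rule meant to remove badly timed samples could then remove samples drawn on time or slightly early, in one season and one product. By the authorisations described in Protocol 1.1, BNT162b2 is the only product open to ages 5 to 17, so children in a first-season primary series would be among those exposed.

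The second issue is that nothing in EO7 or EO8 says how the seasons are handled. For HAI, both the draw day and the IIV4 strains can differ by season. For SARS-CoV-2 neutralisation, Protocol 3.1 allows variant-containing COVID-19 vaccines to enter later. If the seasons are analysed together with no season term, that variation stays in the residual error of the between-arm comparison.

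**Working it through.** The plan states no accepted day range for these samples, so there is no figure of its own to reproduce. Its one power figure, 82.6% for the primary endpoint, does not enter this point.

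**Inputs**
- Day numbering: Protocol 3.1 makes the vaccination day Day 1, so study day = days after vaccination + 1. Protocol Table 5 agrees, pairing Day 29 with 28 days.
- Current protocol window: 28 ± 4 days, that is 24 to 32 days (Table 5; Visit 3 after Visit 1, Visit 4 after Visit 2).
- Sample limit: -7/+14 days (SAP 6.3 and Appendix 1).
- First-season draw: Day 21. This is either 21 days after vaccination (study Day 22, the Protocol 6.2 wording) or literal study Day 21 (20 days after vaccination).

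**Step 1. Accepted range, in days after vaccination**
- A. Day 29 target applied to the first season: 28 - 7 = 21 and 28 + 14 = 42, which is study Days 22 to 43.
- B. Appendix 1, current protocol window widened: 24 - 7 = 17 and 32 + 14 = 46.
- C. First-season target used: 21 - 7 = 14 and 21 + 14 = 35. If Day 21 means 20 days, 20 - 7 = 13 and 20 + 14 = 34.

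**Step 2. Is a draw made exactly on schedule accepted?** The margin is the draw day minus the lower limit.

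| Reading | Drawn 21 days after vaccination | Drawn on study Day 21 (20 days after) |
|---|---|---|
| A | In, 21 - 21 = 0, on the limit | Out, 20 - 21 = -1 |
| B | In, 21 - 17 = 4 | In, 20 - 17 = 3 |
| C | In, 21 - 14 = 7 | In, 20 - 13 = 7 |

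Exclusion of an on-schedule draw occurs in one cell of six. Reading A nevertheless leaves no early allowance where the rule intends seven days.

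**Step 3. Draws slightly off schedule.** Assume that the first-season visit also allowed ± 4 days; the documents do not say so. A 21-day target then gives draws at 17 to 25 days, and a 20-day target gives 16 to 24.
- Reading A excludes draws at 17 to 20 days, or 16 to 20 with literal numbering.
- Reading B excludes none, or only day 16 with literal numbering.
- Reading C excludes none.

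**Step 4. Safety net.** The additional analysis in SAP 6.3 starts when 10% of the study population is excluded for timing: 0.10 × 450 = 45 people. First-season BNT162b2 primary-series enrolment is not given, so the share affected cannot be computed. If fewer than 45 are excluded in total, no additional analysis follows.

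**Step 5. Season in the models**

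| Analysis | Terms or strata listed | Season or draw day |
|---|---|---|
| EO7 regression | None | Not listed |
| EO8 regression | Platform, site | Not listed |
| Mantel-Haenszel tests, EO7 and EO8 | Site | Not listed |

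The documented draw-day change concerns serum stored for HAI. Neutralisation draws follow Protocol 5.1, where Table 5 shows only 28 ± 4 days. The case for a season term in EO8 therefore rests on a possible change of COVID-19 vaccine formulation, not on draw day. The gain in precision cannot be sized, because no titre variance by season is given.

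**The case against.** A reader might infer that all on-schedule first-season samples fall out of window. The documents do not support that. SAP 6.3 refers to the time frame that the protocol defines for the respective vaccine, and for these participants Protocol 3.2.1 defines Day 21. Appendix 1, which lists the actual exclusions, keeps the sample on either numbering, and the elapsed-time wording of Protocol 6.2 keeps it even against Day 29. This part of the objection stands: the loss is conditional on one combination of readings. What remains is that the SAP never states the first-season target, and its two window rules give different ranges.

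A reader might also infer that the seasons are pooled without adjustment. The SAP is silent on pooling, and both documents speak of comparing HAI for the strains in each season's vaccine, which points partly towards season-specific comparison. That does not settle the matter, because Protocol 6.2 names only the 2021-22 antigens for testing sera from all participants. The supported statement is that the method of combining seasons is unspecified.

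The two consequences are also alternatives for on-schedule samples. If they are removed, they cannot mix three-week with four-week titres; if they are kept, they can.

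Finally, EO7 and EO8 are exploratory, HAI testing depends on further funding (Protocol 6.2), booster recipients are at Day 29 throughout, and Protocol 1.2 expects most adults and many children to be booster recipients. All of this stands and limits the weight of the point.

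**Conclusion.** The conflict is real and limited in scope. Protocol 3.2.1 has two draw days for BNT162b2 primary-series participants and SAP 4.2.1 has one. Depending on which SAP sentence is followed, the accepted range for a first-season sample is 21 to 42, 17 to 46, or about 14 to 35 days after vaccination. An exactly on-schedule draw is lost, by one day, only if Day 29 is imposed on the first season and Day 21 is read as 20 elapsed days. On the 21-day reading it is kept, but with no early allowance. The number at risk is unknown.

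Season and draw day are absent from the stated EO7 and EO8 analyses. Bias between arms would be too strong an inference: Protocol 5.2.1 randomises 1:1 in permuted blocks within site, age group and vaccine series, so season and draw day should be roughly balanced. The cost is in retained samples, comparability of titres and precision. The primary endpoint and its stated power are unaffected.

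**What to change.** In SAP 4.2.1, 6.3 and Appendix 1:
- State the target draw day by product, series and season as the protocol gives it: Day 21 for the BNT162b2 primary series in 2021-22, Day 29 otherwise. Say whether Day 21 is a study day or 21 elapsed days.
- Use one definition of the -7/+14 window in both places, anchored to that target.

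In SAP 8.3:
- Add influenza season as a covariate in the EO7 and EO8 regressions, or analyse by season where the strains differ, and say which applies.
- A season stratum in the Mantel-Haenszel tests is optional, because it thins the strata.

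The cost is SAP wording and one extra model term, for a variable already collected under SAP 7.1.
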